11.1 Data Monitoring Committee

An independent DMC will be established to review unblinded safety data and summary reports, identify any safety issues and trends, and make recommendations to AbbVie, including ongoing trial conduct or modifications to the trial, if emerging data show unexpected and clinically significant AEs of treatment.

Details of the DMC memberships, standard operational procedures for data monitoring/review, frequency of review, and other pertinent details will be provided in a separate DMC Charter.

12.0 Overall Type-I Error Control

No multiplicity adjustment for overall Type-I Error Control is planned for this study.

13.0 COVID-19 Related Analyses

This section specifies analyses related to COVID-19 pandemic from the following aspects:

- Disposition
- Study visits and study procedures
- Protocol deviation
- Treatment interruption due to COVID-19
- TEAEs related with COVID-19 and supplemental signs and symptoms
- COVID-19 status (COVID-19 testing results or contact with a COVID-19 positive person)
- COVID-19 vaccination

The Safety Populations 1 and 2 will be used for the planned analyses described above. The number of subjects with study visits impacted by COVID-19 will be summarized. In addition, the number of subjects impacted by COVID-19 and their corresponding

disposition status in the open-label periods and the follow-up period will be summarized respectively.

The number of subjects who missed at least one entire visit, had in person, partial assessment done, and had virtual visits due to COVID-19 will be summarized.

The number of subjects with protocol deviation due to COVID-19 will be provided. The number of subjects with study drug interruption due to COVID-19 will be provided as well. The number of subjects with TEAEs and serious TEAEs related to COVID-19 vaccine will be provided.

Supporting listings for the described analyses above and TEAEs leading to study discontinuation related to COVID-19 will be provided.

14.0 Version History

This Statistical Analysis Plan (SAP) for Study M23-072 is based on the protocol dated 22July2022.

Table 1. SAP Version History Summary

Version	Date	Summary
1.0	31 March 2022	Initial version
2.0	07 December 2022	Corrected typos and removed duplicated paragraphs throughout the document. Changed "double-blind" to "open-label" throughout the document. Updated language throughout the document to align with protocol. Section 2.3 changed Week 1 to Day 1 to be consistent with protocol. Section 3.2 changed Weeks 12 to Weeks 13 to avoid overlap of visits. Section 5.0 deleted 'Participants enrolled (randomized) in the study'. Section 5.0 changed 'follow-up period' to 'study' to correct the analysis of discontinuation period. Section 9.3.2 deleted 'and the p-value'. No need to provide p-value in efficacy analyses for this open-label study.

Version	Date	Summary
		
Added ubrogepant take dose subgroup definition in Section 9.4
 
Removed MMRM model-based analysis for under subgroup analysis for Section 9.4.
 
Removed analysis in AESI section as it's covered in Section 10.3.
 
Added subgroup analysis for safety (Section 10.6).
 
Updated Appendix A to clarify MTOQ6's definition.
 
Updated Appendix B, protocol deviation section to align with standard.
 
Removed Appendix C as AESIs are defined in the SAP body.
 
Updated Appendix index accordingly.
 
Updated mITT 1 and mITT 2 population definitions with "received" instead of "receive" in Section 4.0.
 
Added that baseline analyses are done for both Safety Population 1 and Safety Population 2 in Section 4.0.
 
Reorganized the subject categories in Section 5.0. Deleted analyses description that were repeated.
 
Added subject accountability by investigator in Section 5.0.
 
Clarified definition for duration of treatment for both atogepant and ubrogepant and the analysis populations in Section 6.0.
 
Specified demographic groups in Section 7.1. Added "migraine prevention medication in the past" to disease characteristics (migraine history) in Section 7.1.
 
Added definitions for concomitant medication for each period in Section 7.3.
 
Updated in Section 9.2 that efficacy analyses are based on observed case (OC).
 
Clarified the meaning of patient satisfaction responder in Section 9.3.2.
 
In Section 9.4, added details about efficacy subgroup analyses and the analysis populations.
 
Deleted MedDRA version in Section 10.2.1 as it's repeated.
 
Specified that study drug include atogepant and ubrogepant in Section 10.2.2.
 
Added analyses detail for Section 10.2.3 (TEAE by SOC & PT), Section 10.2.4 (SAE & AE leading to study drug discontinuation), and Section 10.3 (laboratory data).
 
Clarified potential Hy's law analysis in Section 10.3
 
For Section 13.0, deleted efficacy evaluation under COVID-19 related analyses, specified the analysis populations, added TEAE leading to study discontinuation related to COVID-19.

Version	Date	Summary
		Moved ECG post-baseline values of clinical interest to appendix Table 8 (newly added). Changed the table numbering accordingly.

Appendix A. Derivation of Efficacy Variables

A.1 Derivation of Health Outcome Endpoints

MSQ Related Endpoints Derivation

MSQ v2.1 consists of 14 items with a 4-week recall period. The scoring of the MSQ is completed in following 3 steps.

Step 1: Final item value assignment.

Precoded item values and final item values for each MSQ item response are shown in Table 2.

Table 2. Item Values for MSQ Item Responses

Response Categories	Precoded Item Value	Final Item Value
None of the time	1	6
A little bit of the time	2	5
Some of the time	3	4
A good bit of the time	4	3
Most of the time	5	2
All of the time	6	1

Step 2: Computation of raw domain (dimension) scores

Once a final item value has been assigned to each item, a raw score can be computed for each MSQ domain. Role Function Restrictive domain includes Items 1 - 7, Role Function Preventive domain includes Items 8 - 11, and Emotional Function domain includes Items 12 - 14. The raw score for each domain is the algebraic sum of the final item values for all items in that domain.

Missing data handling: if a respondent answered at least half of the items in a domain (or half plus one in the case of scales with an odd number of items), a

missing item value can be estimated using the average of the other completed items within the same dimension.

In detail, for MSQ v2.1 Role Function Restrictive domain, the 7 individual item responses using final item value will be summed, resulting in the raw domain score ranging from 7 to 42 with higher scores indicating better quality of life. If there are missing item responses, the raw domain score will be calculated by summing the non-missing item responses using final item value and dividing by the number of non-missing items and then multiplying by 7 provided that 4 or more items in the domain are completed; otherwise it will be set to missing. For MSQ v2.1 Role Function Preventive and Emotional domains, the raw domain scores will be calculated similarly using final item value respectively. If there are missing item responses, the corresponding raw domain score will be calculated by summing the non-missing item responses using final item value and dividing by the number of non-missing items and then multiplying by the number of questions in that domain provided that 2 or more domain items are completed; otherwise it will be set to missing.

Step 3: Linear transformation to a 0 to 100 scale.

The transformation formula for each MSQ 2.1 domain is listed below

- Role Function -Restrictive:
$$\frac{(raw\ score - 7) * 100}{35}$$
- Role Function-Preventive:
$$\frac{(raw\ score - 4) * 100}{20}$$
- Emotional Function:
$$\frac{(raw\ score - 3) * 100}{15}$$

HIT-6 Total Score Derivation

For HIT-6 total score, pre-coded item values and final item values for each item response are shown in Table 3. Total score is calculated by summing 6 sub-item responses, resulting in the total score ranging from 36 to 78 with higher scores indicating greater impact. If any sub item is missing, then total score will be missing.

Table 3. Item Values for HIT-6 Item Responses

Response Categories	Precoded Item Value	Final Item Value
Never	0	6
Rarely	1	8
Sometimes	2	10
Very Often	3	11
Always	4	13

The HIT-6 instrument has a recall period of 4 weeks for 3 of the 6 items.

Patient Health Questionnaire (PHQ-4)

The PHQ-4 is a 4-item patient health questionnaire for anxiety and depression. Subjects are asked to indicate the frequency with which they have been bothered by 4 symptoms of depressive disorders over the previous 2 weeks, on a 4-point scale: 0 (not at all), 1 (several days), 2 (more than half the days), and 3 (nearly every day). The total score ranges from 0 to 12 (from best to worst). A Total Score will be calculated using (sum of non-missing items) \times 4 / (number of non-missing items) if 3 or more items scores have non-missing responses.

MTOQ 6 Score Derivation

The MTOQ-6 is a 6 question, Likert-type, self-reporting questionnaire with responses ranging from "never" to "half the time or more" with the following response scores: Never = 1, Rarely = 2, Less Than Half The Time = 3, Half The Time Or More = 4. The total score for the MTOQ-6 is the sum of each response score and will be treated as missing if the response is missing for one or more questions.

WPAI:MIGRAINE Related Endpoints Derivation

WPAI outcomes are expressed as impairment percentages, with higher numbers indicating greater impairment and less productivity, i.e., worse outcomes, as follows:

Questions:

- Q1 = currently employed (working for pay).
- Q2 = missed work hours because of problems associated with your migraine
- Q3 = missed work hours due to other reason.
- Q4 = hours actually worked.
- Q5 = migraine affected productivity while working.
- Q6 = migraine affected regular daily activity.

Scores:

Multiply scores by 100 to express in percentages.

- Percent work time missed due to migraine (absenteeism): $Q2/(Q2 + Q4) \times 100$
- Percent impairment while working due to migraine (presenteeism): $Q5/10 \times 100$
- Percent overall work impairment due to migraine (overall work productivity loss): $Q2/(Q2 + Q4) + (1 - (Q2/(Q2 + Q4))) \times (Q5/10) \times 100$
- Percent activity impairment due to migraine (regular activity impairment): $Q6/10 \times 100$

If the response to Q1 ("Currently employed?") is No or missing, absenteeism, presenteeism, and overall work productivity loss will all be set to missing.

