3.2 Exploratory Efficacy Endpoint(s)

- Change from baseline in mean monthly migraine days, headache days, and acute medication use days across Weeks 1 to 12, Weeks 13 to 24, and at each 4-week interval.

- Achievement of at least $\geq 25\%$, $\geq 50\%$, $\geq 75\%$, and 100% reduction in mean monthly migraine days across Weeks 1 to 12, Weeks 13 to 24, and at each 4-week interval.
- Percentages of migraine attacks treated with ubrogepant that result in pain freedom at 2 hours, pain relief at 2 hours, sustained pain freedom from 2 to 24 hours, and sustained pain relief from 2 to 24 hours across Weeks 13 to 24, and at each 4-week interval.
- Patient satisfaction with atogepant at Week 12 and Week 24.
- Patient satisfaction with ubrogepant, taken as needed, at Week 24.
- Patient satisfaction with the concomitant use of atogepant and ubrogepant (taken as needed) at Week 24.
- Change from baseline in the Headache Impact Test (HIT)-6 total score at Weeks 4, 8, 12, 16, 20, and 24.
- At least a 5-point improvement (decrease) from baseline in HIT-6 total score at Weeks 4, 8, 12, 16, 20, and 24.
- Patient Global Impression of Change (PGIC) of "much better" or "very much better" at Week 12 (atogepant) and Week 24 (atogepant + ubrogepant).
- Change from baseline in percent work time missed, percent impairment while working, percent overall impairment, and percent activity impairment due to migraine at Weeks 4, 8, 12, 16, 20, and 24 as assessed by the Work Productivity and Activity Impairment Questionnaire: Migraine (WPAI:MIGRAINE).
- Change from baseline in the Migraine-Specific Quality-of-Life Questionnaire (MSQ) v2.1 Role Function-Preventive domain score at Weeks 4, 8, 12, 16, 20, and 24.
- Change from baseline in the MSQ v2.1 Role Function-Restrictive domain score at Weeks 4, 8, 12, 16, 20, and 24.
- Change from baseline in the MSQ v2.1 Emotional Function domain score at Weeks 4, 8, 12, 16, 20, and 24.
- Change from baseline in the Patient Health Questionnaire (PHQ)-4 score at Weeks 4, 8, 12, 16, 20, and 24.

- Migraine Treatment Optimization Questionnaire (MTOQ)-6 score at Weeks 16, 20, and 24.

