9.3.2 Analysis of Exploratory Efficacy Endpoints

Continuous Endpoints

The change from baseline in mean monthly migraine days, headache days, and acute medication use days across Weeks 1 to 12, Weeks 13 to 24, and at each 4-week interval will be analyzed using a mixed-effect model for repeated measures (MMRM) for each period (open-label atogepant period or open-label atogepant + ubrogepant period), including visit as a categorical fixed effect, and baseline value and baseline-by-visit interaction as covariates. An unstructured covariance matrix will be used to model the covariance of within-subject repeated measurements. The Kenward-Roger approximation will be used to estimate the denominator degrees of freedom. The analysis will be performed based on postbaseline values using only the observed cases without imputation of missing values. Contrasts will be constructed to obtain the average treatment effects across the 12-week period for Weeks 1 to 12 or Weeks 13 to 24. The treatment effect (across the 12-week period for Weeks 1 to 12 or Weeks 13 to 24, and at each 4-week

interval) will be estimated by the least square (LS) Means, the standard error (SE) and 95% confidence intervals.

(HIT)-6 total score is derived as specified in the Appendix A. The change from baseline for (HIT)-6 total score will be analyzed similarly as above using MMRM.

The percent work time missed, percent impairment while working, percent overall impairment, and percent activity impairment due to migraine at Weeks 4, 8, 12, 16, 20, and 24 as assessed by the Work Productivity and Activity Impairment Questionnaire: Migraine (WPAI:MIGRAINE) are derived as specified in Appendix A. The change from baseline for these endpoints will be analyzed similarly as above using MMRM.

MSQ Role Function-Preventive domain score, Role Function-Restrictive domain score and Emotional Function domain score are derived as specified in Appendix A. The change from baseline for these endpoints will be analyzed similarly as above using MMRM.

(PHQ)-4 score is derived as specified in Appendix A. The change from baseline for (PHQ)-4 will be analyzed similarly as above using MMRM.

The MTOQ-6 score is derived as specified in Appendix A. The MTOQ-6 score will be summarized by visit.

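### The WPAI overall work impairment formula in SAP Appendix A lacks an outer bracket, so as printed it scores every visit with migraine-related missed work hours too low

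*SAP*

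**What the plan says.** Among the exploratory endpoints, assessed every four weeks up to Week 24, SAP Section 3.2 (like protocol Section 3.3) lists "Change from baseline in percent work time missed, percent impairment while working, percent overall impairment, and percent activity impairment due to migraine". Section 9.3.2 analyses these changes by MMRM and makes Appendix A the scoring rule ("WPAI:MIGRAINE) are derived as specified in Appendix A").

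The WPAI part of Appendix A.1 first fixes scale and direction: "WPAI outcomes are expressed as impairment percentages, with higher numbers indicating greater impairment and less productivity, i.e., worse outcomes". It defines the inputs, among them "Q2 = missed work hours because of problems associated with your migraine", and places a general instruction above the formulas: "Multiply scores by 100 to express in percentages". The formulas that matter here are:

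- absenteeism: Q2/(Q2 + Q4) x 100
- presenteeism: Q5/10 x 100
- overall work impairment: "Q2/(Q2 + Q4) + (1 - (Q2/(Q2 + Q4))) \times (Q5/10) \times 100"

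If the employment question is answered no or left blank, "absenteeism, presenteeism, and overall work productivity loss will all be set to missing".

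**The concern.** Absenteeism and presenteeism each carry a factor of 100 that covers the whole expression. In the overall score the same factor covers only the second term, because no bracket encloses the sum. The absenteeism part therefore enters at one hundredth of its intended weight.

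This is more than a scaling blemish. Missed time also appears in the second term, through the factor (1 - A), and there it reduces the score. Once its positive contribution has been shrunk to almost nothing, the negative one dominates, and the score falls as missed work rises. An analyst who follows the SAP literally would report a change from baseline that counts less missed work as a worsening for anyone with Q5 of 1 or more.

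The score would also enter the interim analysis (protocol Section 7.6, SAP Section 11.0). That analysis covers all efficacy endpoints and is meant to support access and reimbursement negotiations, so a wrong figure could be used before the final report.

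**Working it through.** **Inputs.** Q2 (hours missed because of migraine), Q4 (hours worked) and Q5 (effect of migraine on productivity while working, divided by 10 in the formula) come from SAP Appendix A.1. Hours missed for other reasons (Q3) do not enter the formula. The plan gives no worked example or numerical value for this score, so there is no figure of its own to reproduce. The hours used below are illustrative.

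**Formulas.** Let A = Q2/(Q2+Q4) and P = Q5/10.

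- As printed: A + 100 x (1 - A) x P
- On the appendix's percentage scale: 100 x [A + (1 - A) x P] = 100A + 100 x (1 - A) x P
- Bracketed minus printed: 100A - A = 99A, independent of Q5

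A numerical comparison over Q2 and Q4 from 0 to 40 hours in steps of 2 (excluding Q2 + Q4 = 0) and Q5 from 0 to 10 agreed with 99A at every point to rounding error.

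**Direction.** The slope in A is 1 - 10 x Q5 for the printed form: +1 at Q5 = 0, -9 at Q5 = 1, -49 at Q5 = 5. For the bracketed form it is 100 - 10 x Q5, which is never negative. So the printed score falls with more missed work for every Q5 of 1 or more. At Q5 = 0 the order is kept but the scale is wrong.

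**Scores.**

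| Q2, Q4, Q5 | A | Printed | Bracketed | Shortfall |
|---|---|---|---|---|
| 0, 40, 5 | 0 | 50.0 | 50.0 | 0 |
| 2, 38, 3 | 0.05 | 0.05 + 0.95 x 30 = 28.55 | 5 + 28.5 = 33.5 | 4.95 |
| 4, 36, 5 | 0.10 | 0.1 + 0.9 x 50 = 45.1 | 10 + 45 = 55.0 | 9.9 |
| 8, 32, 5 | 0.20 | 0.2 + 0.8 x 50 = 40.2 | 20 + 40 = 60.0 | 19.8 |
| 20, 20, 5 | 0.50 | 0.5 + 0.5 x 50 = 25.5 | 50 + 25 = 75.0 | 49.5 |
| 32, 8, 5 | 0.80 | 0.8 + 0.2 x 50 = 10.8 | 80 + 10 = 90.0 | 79.2 |
| 40, 0, 5 | 1.00 | 1.0 | 100.0 | 99.0 |

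**Internal check.** A + (1 - A) x P can never be smaller than P. Yet for (8, 32, 5) the appendix's own list gives presenteeism 50 and printed overall impairment 40.2.

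**Change from baseline.** Printed change minus bracketed change = 99 x (A at baseline - A at visit).

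| Baseline to visit | Printed change | Bracketed change | Difference |
|---|---|---|---|
| (8, 32, 5) to (2, 38, 3) | 28.55 - 40.2 = -11.65 | 33.5 - 60.0 = -26.5 | 99 x 0.15 = 14.85 |
| (8, 32, 5) to (0, 40, 5) | 50.0 - 40.2 = +9.8 | 50.0 - 60.0 = -10.0 | 99 x 0.20 = 19.8 |
| (32, 8, 5) to (2, 38, 3) | 28.55 - 10.8 = +17.75 | 33.5 - 90.0 = -56.5 | 99 x 0.75 = 74.25 |

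The last two rows reverse the sign. The third is an extreme case, with 80% of work time missed at baseline.

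**Mean effect.** Percent work time missed is 100A. In raw means, among subjects with both scores, each 1-point fall in it hides 0.99 points of improvement in overall impairment. Assuming a mean fall of 1 to 10 points, the understatement is 0.99 to 9.9 points; with no mean change in missed time it is 0.

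**The case against.** The best defence is that the intended score can be recovered from the surrounding text. The line is labelled as a percentage, the absenteeism formula scales the same first term correctly, and the general instruction to multiply by 100 can be read as applying to the whole score. An experienced programmer would probably supply the bracket, and nothing in the documents shows how the score was programmed.

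That makes the intention clear, but it does not repair the line. Every formula in the list already carries its own factor of 100; applying the general instruction to the printed formula as well would give 100 x 40.2 = 4020 for (8, 32, 5). A programmer must either reproduce the error or depart from the SAP.

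Three further points stand as limits:

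- An outer bracket may have been lost when the PDF text was extracted. The remaining brackets balance, which makes this less likely but does not exclude it.
- The 0.99 factor is exact for raw means. The planned MMRM estimate, on observed cases with baseline terms, need not reproduce it exactly when visits are missing.
- This is one of four WPAI scores, and the other three formulas are correct. The endpoint is exploratory, without multiplicity control.

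**Conclusion.** The formula is wrong as printed. Followed literally, it understates overall work impairment by 99 x Q2/(Q2+Q4) points at every visit with migraine-related missed hours. It also reverses the effect of missed work for Q5 of 1 or more, and it can reverse the sign of a subject's change from baseline. The algebra rests on no assumption beyond ordinary operator precedence.

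The size of the effect in this trial cannot be determined, because the documents give no distribution of missed hours. The 0.99 to 9.9 point range depends on the assumed mean fall in percent work time missed. Visits with Q2 = 0 are scored correctly, and subjects not in paid work have no score. The primary safety objective is untouched. The line should still be corrected, because it is the only scoring rule the plan gives for a listed endpoint.

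**What to change.** Replace the line with 100 x { Q2/(Q2+Q4) + [1 - Q2/(Q2+Q4)] x (Q5/10) }. Check the source SAP in case the bracket is present there, and confirm that the derivation program, including any version used for the interim analysis, applies the bracketed form. State that the factor of 100 is applied once, so that the general scaling instruction is not added to formulas that already contain it.

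The cost is one bracket in the SAP and one program check. Data collection and design do not change.

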Appendix B. Protocol Deviations

The number and percentage of subjects who reported at least one of the following protocol deviation categories will be provided for the Safety Population 1.

- Subject entered into the study even though s/he did not satisfy entry criteria.
- Subject developed withdrawal criteria during the study and was not withdrawn.
- Subject received wrong treatment or incorrect dose of study.
- Subject took prohibited concomitant medication.

Appendix C. Potentially Clinically Significant Criteria for Safety

The potentially clinically significant criteria for clinical laboratory parameters, vital signs and ECG parameters are provided in the following tables.

Clinical laboratory parameters are provided in the following tables.

Table 4. Potentially Clinically Significant Criteria for Clinical Laboratory Parameters

Category	Parameter	SI Unit	PCS Criteria	
			PCS Low	PCS High
Chemistry	Albumin	g/L	< 0.8 × LLN	> 1.2 × ULN
	Alanine aminotransferase	U/L	—	≥ 3.0 × ULN
	Alkaline phosphatase	U/L	—	≥ 3.0 × ULN
	Aspartate aminotransferase	U/L	—	≥ 3.0 × ULN
	Bicarbonate	mmol/L	< 0.9 × LLN	> 1.1 × ULN
	Bilirubin, total	µmol/L	—	≥ 1.5 × ULN
	Blood urea nitrogen	mmol/L	—	> 1.5 × ULN
	Calcium	mmol/L	< 0.9 × LLN	> 1.1 × ULN
	Chloride	mmol/L	< 0.9 × LLN	> 1.1 × ULN
	Cholesterol, total	mmol/L	—	> 1.6 × ULN
	Creatinine	µmol/L	—	> 1.5 × ULN
	Creatine kinase	U/L	—	> 2.0 × ULN
	Estimated glomerular filtration rate	mL/min/1.73m ²	< 60 mL/min/1.73m ²	—
	Glucose, nonfasting	mmol/L	< 0.8 × LLN	> 2.0 × ULN
	Lactate dehydrogenase (LDH)	U/L	—	> 3.0 × ULN
	Phosphorus	mmol/L	< 0.9 × LLN	> 1.1 × ULN
	Potassium	mmol/L	< 0.9 × LLN	> 1.1 × ULN
	Protein, total	g/L	< 0.9 × LLN	> 1.1 × ULN
	Sodium	mmol/L	< 0.9 × LLN	> 1.1 × ULN
	Triglycerides	mmol/L	—	> 2.0 × ULN
	Uric acid	µmol/L	—	> 1.2 × ULN

Category	Parameter	SI Unit	PCS Criteria	
			PCS Low	PCS High
Hematology	Basophils, absolute cell count	10 ⁹ /L	—	> 2.0 × ULN
	Eosinophils, absolute cell count	10 ⁹ /L	—	> 2.0 × ULN
	Hematocrit	Ratio	< 0.9 × LLN	> 1.1 × ULN
	Hemoglobin	g/L	< 0.9 × LLN	> 1.1 × ULN
	Lymphocytes, absolute cell count	10 ⁹ /L	< 0.7 × LLN	> 1.3 × ULN
	Monocytes, absolute cell count	10 ⁹ /L	< 0.5 × LLN	> 2.0 × ULN
	Neutrophils, absolute cell count	10 ⁹ /L	< 0.7 × LLN	> 1.3 × ULN
	Platelet count	10 ⁹ /L	< 0.5 × LLN	> 1.5 × ULN
	Red blood cell count	10 ¹² /L	< 0.9 × LLN	> 1.1 × ULN
	White blood cell count	10 ⁹ /L	< 0.9 × LLN	> 1.5 × ULN
Urinalysis	pH	pH	< 0.9 × LLN	> 1.1 × ULN
	Glucose	mmol/L	—	Positive ¹
	Protein	g/L	—	Positive ²
	Specific gravity	—	—	> 1.1 × ULN

LLN = lower limit of normal value; ULN = upper limit of normal value; normal value provided by laboratory; SI = Le Système International d'Unités (International System of Units)

1. Any results other than negative will be considered as positive.
2. Any results other than trace or negative will be considered as positive.

Table 5. Criteria for Hepatic Laboratory Abnormalities

Laboratory Parameter	Categories
ALT	≥ 1 × ULN
	≥ 1.5 × ULN
	≥ 2 × ULN
	≥ 3 × ULN
	≥ 5 × ULN
	≥ 10 × ULN
	≥ 20 × ULN

Laboratory Parameter	Categories
AST	$\geq 1 \times \text{ULN}$
	$\geq 1.5 \times \text{ULN}$
	$\geq 2 \times \text{ULN}$
	$\geq 3 \times \text{ULN}$
	$\geq 5 \times \text{ULN}$
	$\geq 10 \times \text{ULN}$
	$\geq 20 \times \text{ULN}$
ALT or AST	$\geq 1 \times \text{ULN}$
	$\geq 1.5 \times \text{ULN}$
	$\geq 2 \times \text{ULN}$
	$\geq 3 \times \text{ULN}$
	$\geq 5 \times \text{ULN}$
	$\geq 10 \times \text{ULN}$
	$\geq 20 \times \text{ULN}$
Bilirubin Total	$\geq 1 \times \text{ULN}$
	$\geq 1.5 \times \text{ULN}$
	$\geq 2 \times \text{ULN}$
	$\geq 3 \times \text{ULN}$
	$\geq 5 \times \text{ULN}$
	$\geq 10 \times \text{ULN}$
	$\geq 20 \times \text{ULN}$
Alkaline Phosphatase	$\geq 1 \times \text{ULN}$
	$\geq 1.5 \times \text{ULN}$
	$\geq 2 \times \text{ULN}$
	$\geq 3 \times \text{ULN}$
	$\geq 5 \times \text{ULN}$
	$\geq 10 \times \text{ULN}$
	$\geq 20 \times \text{ULN}$
Concurrent Elevations ¹	ALT or AST $\geq 3 \times \text{ULN}$ and Bilirubin Total $\geq 1.5 \times \text{ULN}$
	ALT or AST $\geq 3 \times \text{ULN}$ and Bilirubin Total $\geq 2 \times \text{ULN}$
Potential Hy's Law ¹	ALT or AST $\geq 3 \times \text{ULN}$ and Bilirubin Total $\geq 2 \times \text{ULN}$ and ALP $< 2 \times \text{ULN}$

ALT = alanine aminotransferase; AST = aspartate aminotransferase; TBL = total bilirubin; ALP = alkaline phosphatase; ULN = upper limit of normal (value provided by the laboratory)

1. Elevations are from the same day.

Vital sign values will be considered PCS if they meet both the observed value criterion and the change from baseline value criterion, if both criteria are available, or meet either the observed value criterion or the change from baseline value criterion that is detailed in the following table.

Table 6. Potentially Clinically Significant Criteria for Vital Signs Parameters

Parameter	Flag	Criteria	
		Observed Value	Change from Baseline
Systolic blood pressure, mm Hg	High	≥ 180	Increase of ≥ 20
	Low	≤ 90	Decrease of ≥ 20
Diastolic blood pressure, mm Hg	High	≥ 105	Increase of ≥ 15
	Low	≤ 50	Decrease of ≥ 15
Pulse rate, bpm	High	≥ 120	Increase of ≥ 15
	Low	≤ 50	Decrease of ≥ 15
Weight, kg	High	—	Increase of $\geq 7\%$
	Low	—	Decrease of $\geq 7\%$
Orthostatic SBP change, mm Hg	Low	≤ -20	—
Orthostatic DBP change, mm Hg	Low	≤ -15	—
Orthostatic Pulse rate change, bpm	High	≥ 25	—

SBP = Systolic blood pressure; DBP = Diastolic blood pressure; bpm = beats per minute

ECG parameter values are considered PCS if ECG values meet either the actual value or change from baseline PCS high criteria listed in the following table.

Table 7. Potentially Clinically Significant Criteria for ECG Parameters

Parameter	Unit	Criterion
QRS interval	msec	≥ 150
PR interval	msec	≥ 250
QTc (QTcB or QTcF) interval	msec	> 500
QTc (QTcB or QTcF) interval	msec	Increase from baseline > 60

Table 8. ECG Post-baseline Values of Clinical Interest

Parameter	Unit	Criterion
QTcF interval	msec	> 450
		> 480
		> 500
		Increase > 30 but ≤ 60
		Increase > 60

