3.0 Endpoints

3.1 Primary Endpoint

The primary endpoint is to assess the safety endpoints, including adverse event (AE) monitoring, vital sign measurements, electrocardiogram (ECG) variables, clinical laboratory testing (hematology, chemistry, and urinalysis), and Columbia Suicide Severity Rating Scale (C-SSRS).

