10.3 Laboratory Data

Data collected from central laboratories, including additional laboratory testing due to an SAE, will be used in all analyses, except for Baseline where SAE-related laboratory assessments on or before the first dose of study drug without timestamp will be excluded. The details for SAE-related laboratory baseline can be found in the SPP. The clinical laboratory tests defined in the protocol (e.g., hematology, clinical chemistry and urinalysis) will be summarized.

Each laboratory variable will be summarized for all time points (starting with Baseline) with the number of non-missing observations, mean and standard deviation, median, Q1, Q3, minimum and maximum. Mean change from baseline to each applicable post-baseline visit will be summarized with the number of observations, baseline mean, and visit mean. The change from baseline mean, standard deviation, median, Q1, Q3, minimum and maximum will be presented for the mean change from baseline. In addition, descriptive statistics for values and changes from the baseline values in conventional units at each assessment time point will be presented for selected clinical laboratory parameters listed in Appendix D. A description of reporting the lab values in conventional units in patient narratives (along with the standard reporting in SI units) is presented at the end of Appendix D.

Changes in laboratory parameters will be summarized using shift tables categorized as low, normal, or high based on the normal ranges of the laboratory used for each sample. A shift table will be provided to summarize shifts from baseline to the final post-baseline value for all lab categories.

Laboratory abnormalities will be evaluated based on potentially clinically significant (PCS) criteria (Table 4). For each laboratory PCS criterion, the number and percentage of subjects who have a laboratory value meeting the criteria will be summarized in Safety Populations 1 and 2 for each treatment period and overall. Listings will be provided to summarize subject-level laboratory data for subjects meeting PCS criteria.

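### The SAP's only PCS criterion for urine specific gravity sets a threshold of at least 1.100, which genuine urine values are not expected to reach, so this row's zero will carry no information

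*SAP*

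**What the plan says.** SAP Appendix C, Table 4 lists four urinalysis parameters. The row for specific gravity reads "Specific gravity — — > 1.1 × ULN": no unit, no PCS Low criterion, and one PCS High criterion expressed as a multiple of the ULN. The table footnote says of the reference limits only "normal value provided by laboratory", so no numeric ULN appears. Nothing elsewhere in the protocol or SAP redefines the rule for this parameter, for example by applying the factor to the excess over water, and Table 4 has no change-from-baseline criterion that could raise a flag by another route.

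SAP Section 10.3 puts the criterion to use: "For each laboratory PCS criterion, the number and percentage of subjects who have a laboratory value meeting the criteria will be summarized", in both safety populations, by treatment period and overall, with a listing of the subjects concerned. Urinalysis is among the safety assessments that make up the primary endpoint (SAP Section 3.1), and the interim analysis repeats all safety analyses (SAP Section 11.0).

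Section 10.3 also plans other summaries of the same data: descriptive statistics at every time point, including the maximum, change from baseline at each visit, and shift tables: "Changes in laboratory parameters will be summarized using shift tables categorized as low, normal, or high based on the normal ranges of the laboratory". The shift table specified there compares baseline with the last post-baseline value.

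**The concern.** A multiplier on the ULN works when a parameter's zero is a natural origin and its values spread over a good part of the scale. Specific gravity is a density ratio with water at 1.000, and its variation lies in the second and third decimals. A 10% margin on the whole value is then far larger than the spread of the parameter itself.

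If the threshold is out of reach, the row's result is fixed before any data are collected. The PCS table would show 0 (0.0%) in each period and overall, at the interim and at the end, and the listing would have no entries. Nothing in the output would distinguish that zero from one that was observed because no subject had an abnormal value.

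**Working it through.** The plan states no derived figure for specific gravity, so there is nothing to reproduce.

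**Inputs**
- Criterion: value > 1.1 × ULN (SAP Appendix C, Table 4).
- ULN: supplied by the laboratory, not given. Assumed range 1.005 to 1.050, central range 1.025 to 1.035.
- Highest genuine urine specific gravity: not given. Assumed range 1.035 to 1.080.
- Reference point: water = 1.000, by definition of the quantity.

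**Step 1: threshold for a given ULN.** Threshold = 1.1 × ULN. The excess ratio is (threshold − 1) / (ULN − 1), that is, how much further above water a value must lie than the ULN does.

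| Assumed ULN | Threshold | Excess of ULN over water | Excess of threshold over water | Ratio |
|---|---|---|---|---|
| 1.005 | 1.1055 | 0.005 | 0.1055 | 21.1 |
| 1.020 | 1.122 | 0.020 | 0.122 | 6.1 |
| 1.025 | 1.1275 | 0.025 | 0.1275 | 5.1 |
| 1.030 | 1.133 | 0.030 | 0.133 | 4.43 |
| 1.035 | 1.1385 | 0.035 | 0.1385 | 3.96 |
| 1.050 | 1.155 | 0.050 | 0.155 | 3.1 |

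The lower bound needs no assumption about the particular laboratory: for any ULN ≥ 1.000, the threshold is at least 1.1 × 1.000 = 1.100.

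**Step 2: the inverse.** For the flag to be able to fire, the ULN must be below (highest urine value) / 1.1.

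| Assumed highest urine value | Fires only if ULN is below |
|---|---|
| 1.035 | 0.941 |
| 1.040 | 0.945 |
| 1.050 | 0.955 |
| 1.060 | 0.964 |
| 1.080 | 0.982 |

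Every limit in the right-hand column is less dense than water, so none can be an upper limit for urine. The break-even is a urine value of 1.100, since 1.100 / 1.1 = 1.000.

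**Step 3: reporting scale.** If the laboratory reports 1030 instead of 1.030, the threshold becomes 1.1 × 1030 = 1133. Both sides scale together and nothing changes.

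**Result.** The expected PCS count for this row is 0 in Safety Population 1 (about 235 planned) and in Safety Population 2 (about 200 planned; 235 × 0.85 = 199.75), with or without a drug effect.

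**What the zero could be taken to mean.** If 0 of 235 were an informative observation, the one-sided 95% upper bound on the rate would be 1 − 0.05^(1/235) = 1.3%; for 0 of 200 it would be 1 − 0.05^(1/200) = 1.5%. The SAP does not plan these bounds. They show only what a reader might wrongly read into the row.

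**The case against.** The strongest reply is that other planned summaries cover specific gravity. This largely stands. A reader of Table 4 alone might infer that specific gravity goes unscreened, but Section 10.3 does not support that. A general drift would show in the by-visit means and changes from baseline, an extreme value in the by-visit maximum, and a raised last value in the shift table. The cover has one gap: a high value at an intermediate visit that later resolves is missed by the specified shift table, and although the by-visit maximum would show it, the number of subjects affected would not be counted.

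A second reply is proportion. Because urinalysis belongs to the primary endpoint, a reader might infer that the primary safety assessment is compromised. The documents do not support that either. Specific gravity is one of 35 parameters in Table 4; it is neither an adverse event of special interest nor a withdrawal criterion, and no test, stopping rule or precision statement depends on it.

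A third reply is that calling the flag impossible for any human urine needs a maximum that the documents do not supply. That is fair. The supportable statement is conditional on genuine values staying at or below 1.100, and a data-entry or unit error could still trip the flag.

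It might also be said that Table 4 is a standard set of multiples. But the table already departs from multiples where they do not suit a parameter: eGFR has an absolute cut-off, and urine glucose and protein are flagged on a positive result. Treating specific gravity separately would be in keeping with it.

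**Conclusion.** The point holds as a small defect in one table row. The criterion is explicit and not redefined elsewhere, and it is not expected to be met by any genuine measurement. The count and listing for this row are therefore settled in advance, and the zero should not be read as evidence of no effect.

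Two assumptions from outside the documents carry this: a laboratory ULN of at least 1.000, and genuine urine values no higher than 1.100. Both leave ample room around the ranges tried above, so the conclusion does not hinge on a particular laboratory. The defect changes no sample size, error rate or other endpoint, and no conclusion of the study rests on it.

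**What to change.** Change one cell of SAP Appendix C, Table 4, in one of two ways:

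- Delete the specific gravity PCS row and rely on the shift table and descriptive statistics already planned in Section 10.3. This needs no new threshold. It leaves a transient high value visible only in the by-visit maximum.
- Have the sponsor replace the 1.1 multiplier with an attainable criterion on the scale where the parameter varies, for example any post-baseline value above the laboratory ULN. This would count transient highs by period. The documents give no basis for a particular margin beyond the ULN, so that choice belongs to the sponsor.

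The cost is one table entry and about one line of programming. Under a replacement rule, some non-specific high values, such as those from dehydration, will be listed. A plain above-ULN rule would also be less strict than the other ULN-based rows in the table, all of which require a margin beyond the limit.
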